We describe all study measures in detail in the study design and procedures sections below and they appear in our appendices. Below is a brief summary of assessments. Purchasing Survey: After obtaining permission from caregivers, a survey will be administered to students after they have made a food or beverage purchase at a school store. The survey will assess participants nutrition knowledge and label awareness, recall, and use, and trust in label information. Frequency of school store visits and sociodemographic characteristics (e.g., age, sex, race/ethnicity, grade level, and height and weight) will also be assessed (see Appendix B for survey). Beverage Frequency Questionnaire: Participants will also complete a beverage frequency questionnaire to assess their consumption of different types of beverages. This questionnaire will be based on the BEVQ-15, a survey instrument that has been validated as an effective tool used to capture changes in beverage consumption. (1-4) (see Appendix E for BEVQ-15). For each beverage category, the questionnaire assesses frequency of consumption and volume typically consumed. (see Appendix D for adapted questionnaire).

Group Modifications

Describe necessary changes that will or have been made to the study instruments for different groups.

None of the survey questionnaires will differ across randomly assigned groups. Regarding the schools that will be enrolled in the study, pairs of matched private/public schools will be randomized to 1 of 3 labeling conditions

Method for Assigning Subjects to Groups

Describe how subjects will be randomized to groups.

Individual participants will not be randomly assigned to groups. Instead, randomization will occur at the school level. Nine schools will be participating in this research and randomization will be stratified based on whether a school is public (n = 6) or private (n = 3). The Penn research team will use a random number generator to randomize schools to one of three labeling conditions, and the Guatemala team will implement the labels based on the randomization assignment.

Administration of Surveys and/or Process

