Students and their caregivers will first be contacted about study participation using a permission letter (see Appendix A) sent either as a printed letter or electronically. The letter will explain that their children may be asked to complete a short survey after making a purchase at the school store. Caregivers who wish to refuse participation can call a number provided in the permission letter. A list will be maintained with the names of students who have permission to participate. Research assistants will consult this list before administering any surveys to ensure the student has permission to participate. Adolescents who consent to participate and have made a purchase from the school store will be given the opportunity to complete a short survey; verbal assent must be obtained prior to enrollment. Research assistants will be stationed at the school stores during the heaviest traffic times (between 10:00am and 1:30pm and 2:30pm and 3:30pm) Monday to Friday and will invite adolescents to participate in the survey after they make a food and/or beverage purchase at the school store. Research assistants will record the item purchased (type of food/beverage) along with brand, quantity, size, and price. In addition, we will administer a survey that includes a validated beverage frequency questionnaire to assess typical beverage intake (Appendix B). Research assistants will also record the number of students who refuse participation along with their gender. The survey is estimated to last approximately 5-10 minutes. Participants will only be eligible to take the survey once.

Data Management

Describe how and who manages confidential data, including how and where it will be stored and analyzed. For instance, describe if paper or electronic report forms will be used, how corrections to the report form will be made, how data will be entered into any database, and the person(s) responsible for creating and maintaining the research database. Describe the use of pseudonyms, code numbers and how listing of such identifiers will be kept separate from the research data.

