Subjects will not be financially compensated for their participation. However, students will be offered a small prize (e.g., school supplies like pens or pencils) as a token of appreciation for their participation.

Study Procedures

Suicidal Ideation and Behavior

Does this research qualify as a clinical investigation that will utilize a test article (ie- drug or biological) which may carry a potential for central nervous system (CNS) effect(s)?

No

Procedures

Research assistants will be stationed at the school stores during the heaviest traffic times (between 10:00am and 1:30pm and 2:30pm and 3:30pm) Monday to Friday and will invite adolescents to participate in the survey after they make a purchase at the school stores. Only after confirming that a student has permission to participate will the survey be administered. They will be offered a small prize (e.g., school supplies like pens or pencils) as a token of appreciation. After the adolescent has provided verbal consent, a research assistant will record the item(s) purchased (type of food/beverage) along with brand, quantity, size, and price. We will also assess frequency of school store visits and sociodemographic characteristics (e.g., age, sex, race/ethnicity, grade level, and height and weight). We will recruit 1500 students (between 12 and 18 years old) to answer a brief 5-10 minute survey after making a purchase at the school store. Nine schools will be participating in this research and randomization will be stratified based on whether a school is public (n = 6) or private (n = 3). The Penn research team will use a random number generator to randomize schools and the Guatemala team will implement the labels based on the randomization assignment (see Appendix F for label designs). In this six-week study, we will receive purchasing data from the schools during two weeks without labels, two weeks when labels are displayed, and two weeks after labels have been removed. Studying purchases after the labels have been removed will enable us to understand whether the labels are educating children over time or whether they primarily alter behavior by being a salient reminder at the point of purchase.

The following documents are currently attached to this item:

There are no documents attached for this item.

Deception

Does your project use deception?

No

Analysis Plan

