include 100% juice). Frequencies and percentages will be used to describe categorical variables such as percent of students purchasing a sugary drink. Medians and interquartile ranges will be reported for continuous variables that exhibit skewness. Data will be descriptively summarized overall and by labeling strategy. All outcomes will be analyzed at the purchase level. The mean volume of sugary drinks at each two-week period will be modeled among the calorie label, text label, and graphic label arms by a linear regression model including intervention arm, two-week period, interactions of period and intervention arm and type of school (private or public) as independent variables. We will conduct exploratory analyses to examine whether usual frequency of sugary drink intake (high versus low) and biological sex moderate label effects. Examining only aggregate sales data could lead to incorrect inferences. Therefore, complementary individual-level survey data on purchases will also be collected. This aggregate/individual-level data combination will improve inferences about label effects. Although stratification by school type guarantees this variable will be balanced across our intervention arms, we are including it as a covariate in the model because it will enhance the precision of estimating intervention effects, as it explains variability in the outcome. The effectiveness of the interventions will be tested by evaluating the null hypothesis that the coefficients of the interactions of period and intervention are 0, indicating no change in the difference in volume of sugary beverages purchased across intervention arms from baseline. To account for clustering of purchases within schools, test statistics will be corrected using the variance inflation factor (VIF) as determined by the estimated intraclass correlation coefficient (ICC) for within school correlation. Primary and secondary outcomes in the calorie, text-based warning label, and graphic warning label arms will each be compared to one another. A Bonferroni-holm correction will be applied to control for multiple comparisons. We do not expect substantial missing data due to the point-of-sale technology we are using. The primary analysis will examine changes in labeled (sugary) and non-labeled beverages. Secondary analyses will examine changes for the following specific beverage categories: sugar-sweetened cola, sugar-sweetened sports drinks, sugar-sweetened lemonades/iced teas/juices, artificially-sweetened drinks (e.g., Diet Coke), milk, 100% fruit juice, unsweetened coffee/tea, and bottled water. For the survey data, we will conduct similar linear regression analyses to compare total mean kcals purchased among intervention arms.

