- The effectiveness of the intervention will be tested by evaluating the null hypothesis that the coefficient of the interaction of time period and intervention is 0, indicating no change in the fluid ounces of SSBs purchased and beverage calories purchased between conditions.
- Regarding the secondary outcomes, we will present the percentage of all transactions and all beverage transactions that include an SSB by condition and time period. To

calculate the total calories per transaction, we will use the Nutrition Facts Panel data of each food or beverage product.

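### Survey outcomes are compared between arms without adjusting for age, sex or grade, although all three are collected and each period surveys different students

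*Protocol*

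**What the plan says.** The Protocol's Analysis Plan sets out the sales model as a "linear regression model including intervention arm, two-week period, interactions of period and intervention arm and type of school (private or public) as independent variables". The survey outcome then gets one sentence: "For the survey data, we will conduct similar linear regression analyses to compare total mean kcals purchased among intervention arms". Neither names a student characteristic. The only modelling use of student variables is in "exploratory analyses to examine whether usual frequency of sugary drink intake (high versus low) and biological sex moderate label effects". That asks whether the effect differs between subgroups; it does not adjust the main comparison.

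The characteristics are collected. Of the Purchasing Survey the Protocol says "sociodemographic characteristics (e.g., age, sex, race/ethnicity, grade level, and height and weight) will also be assessed", and the SAP's Description of data lists demographics in the survey data set.

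On who is surveyed:
- Assistants at the store "will invite adolescents to participate in the survey after they make a food and/or beverage purchase at the school store" (Protocol, Administration of Surveys and/or Process). The same section limits each student to one survey and logs refusals by number and gender.
- The composition of the surveyed sample is controlled only for public versus private school (Protocol, Design).
- Schools are randomised, not students: nine in the Protocol, and two in the SAP's primary analysis, one per condition.
- Survey timing is given in two ways. Design places the surveys in the intervention weeks; Study duration expects them to take all six weeks.

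The SAP's difference-in-differences equation contains condition, period and their interaction. For the survey percentages it states "we will present the percentage of all transactions and all beverage transactions that include an SSB by condition and time period", with no test or adjustment.

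**The concern.** Randomising a handful of schools does not balance the students who happen to be intercepted at the store. Because no student is surveyed twice, a pre/post comparison in the survey compares different students. If the age, sex or grade mix of those surveyed shifts between periods by different amounts in the arms, and these traits are related to calories bought or to choosing an SSB, the shift is read as a label or poster effect. If surveys are taken only while labels are displayed, there is no survey baseline, and any mix difference between arms enters directly.

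At stake are secondary outcomes, but ones the plan leans on. Total calories is the Protocol's measure of whether students compensate with other snacks, and the survey is meant to guard against wrong conclusions from aggregate sales. The Protocol adjusts for school type because that variable explains variation in the outcome. The same reasoning applies to age, sex and grade.

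**Working it through.** **1. The plan's own figure.** The Protocol (Accrual) gives 500 students per condition, a difference of 0.21 SD and 82% power. Alpha is not stated; two-sided 0.05 is assumed, with Holm over three comparisons.
- Standardised difference: 0.21 / √(2/500) = 0.21 / 0.0632 = 3.32.
- One comparison at 0.05/3: critical value 2.394, so power = Φ(3.32 − 2.394) = 82.3%.
- All three comparisons with Holm, means at 0, 0.21 and 0.42 SD, by simulation: 82.6%.

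The 82% reproduces. It assumes independent students and no covariates.

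**2. How student mix enters the contrast.** Take a binary trait with an effect of b SD on the outcome.
- Surveys in one period only: distortion = b × (difference between arms in the share with the trait).
- Surveys before and during labels: distortion = b × (change in share in one arm − change in share in the other).

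In the second case, shares of 60% and 50% that stay at 60% and 50% contribute nothing. Shares that move from 60% to 70% in one arm and stay at 50% in the other contribute b × 0.10.

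**3. Size.** The documents give neither b nor the shares, so both are assumed. Entries are in SD, with the percentage of 0.21 SD in brackets.

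| Trait effect b | 5 points | 10 points | 20 points | 30 points |
|---|---|---|---|---|
| 0.1 SD | 0.005 (2%) | 0.010 (5%) | 0.020 (10%) | 0.030 (14%) |
| 0.2 SD | 0.010 (5%) | 0.020 (10%) | 0.040 (19%) | 0.060 (29%) |
| 0.3 SD | 0.015 (7%) | 0.030 (14%) | 0.060 (29%) | 0.090 (43%) |
| 0.5 SD | 0.025 (12%) | 0.050 (24%) | 0.100 (48%) | 0.150 (71%) |

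In calories, an assumed 60-kcal gap between the sexes and a net 10-point difference in the share of boys give 60 × 0.10 = 6 kcal. Gaps of 30 to 100 kcal with 5 to 20 points give 1.5 to 20 kcal. In a comparison with a baseline, the point differences must be read as differential changes, not as standing differences between arms.

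**4. Precision.** Let the covariates explain an assumed share R² of the outcome variance.
- Without clustering, joint Holm power rises from 82.6% to about 83.7% (R² = 2%), 85.2% (5%) or 87.7% (10%).
- With 1500/9 ≈ 167 students per school and an assumed intraclass correlation of 0.01, the design effect is 1 + (166.7 − 1) × 0.01 = 2.66. Joint Holm power is then about 18%, and R² = 10% lifts it to about 24%.

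The gain is real but small, and clustering matters far more for power.

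**The case against.** The strongest defence is that both documents test an interaction of period with condition. A lasting difference between schools in age, sex or grade largely cancels there, and the SAP says that it will summarise secondary outcomes before and after. That stands, and it removes most of the worry about fixed differences between schools. It does not cover a change in who is intercepted, and it fails altogether if the surveys fall only in the intervention weeks, as the Protocol's Design section says.

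It can also be said that the sales outcomes are untouched, that sex appears in a moderation analysis, that the SAP tabulates demographics as a data check, and that the precision gain is slight. All true. They limit the weight of the point but do not supply the missing adjustment.

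Two stronger readings are tempting.

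- A reader might infer that assistants see what was bought before choosing whom to invite, or that students who bought an SSB beside a warning refuse more often. The documents say only that the invitation follows the purchase, and the Protocol's Procedures section has the items recorded after verbal consent. Nothing states that the items are seen first, and no acceptance rates are given, so any figure for label-driven refusal would rest on invented inputs.
- A reader might infer that the till shows the true mix and that surveyed purchases should be weighted to it. The listed till fields describe the date and the product, not the student, so they show product mix only. Weighting to the till SSB share would make the SAP's percentage of surveyed transactions with an SSB equal the till figure by construction. It would conflict with standardising for age and sex. It would also target a different population, since the till covers repeat purchases and all hours while surveys are taken once per student in set hours.

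**Conclusion.** The plan leaves out adjustment for age, sex and grade in the survey comparisons, although the data are collected and a label cannot change them. The consequence is a risk of distortion, not a demonstrated bias. It needs a differential change in who is surveyed, or surveys confined to the intervention weeks, together with traits that predict the outcome. Under the assumed ranges the distortion runs from negligible (2% of the 0.21 SD target) to serious (71%), with a middle case of 29% (0.3 SD, 20 points). The precision gain is about 1 to 5 points of power without clustering.

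Adjustment has limits. It removes only what these variables explain, it does not remove selection on the purchase itself, and with one school per condition it cannot separate school from condition.

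**What to change.** 1. In the survey calorie model, add age, sex and grade to the existing terms. Leave out usual intake: it is reported after the purchase, possibly with labels on display, so the label could affect the answer.
2. In the SAP, present both survey SSB percentages raw and, alongside, adjusted or standardised to one age, sex and grade mix.
3. State in which weeks surveys are taken, reconciling the Protocol's Design and Study duration sections. Without surveys before the labels there is no baseline contrast for the survey outcomes.
4. As checks only, report refusals by arm and period, and compare the surveyed SSB share with the till share. Do not weight to the till. The till covers other hours and repeat purchases, so a gap is a prompt for caution, not proof of bias.

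The cost is a little extra analysis and a short rule for students who skip a demographic question. No new data are needed, provided that the SAP's survey data set holds the age, sex and grade items listed in the Protocol.

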## **Analysis Plan: Preventing non-communicable diseases in Guatemala through sugary drink reduction**

### **Aims:**

The primary aim of this study is to test the association between SSB warning/non-SSB promotion posters compared to control posters and 1) changes in mean fluid ounces of SSBs purchased and 2) changes in total beverage calories purchased by adolescents in school cafeterias in Guatemala City.

### **Hypotheses:**

Compared to the counterfactual (what would have happened to purchased fluid ounces and total beverage calories if the SSB warning posters had not been implemented, taking into account pre-treatment differences),

- 1) SSB warning/non-SSB promotion posters are associated with greater reduction in mean fluid ounces of SSB purchased
- 2) SSB warning/non-SSB promotion posters are associated with greater reduction in total beverage calories purchased

### **Primary outcomes:**

1. Fluid ounces of SSBs purchased per sales transaction
  - a. SSBs= any beverage with more than 5g/100mL of sugar reported in the NFP
2. Total beverage calories purchased per sales transaction
  - a. Beverage calories= any calories coming from beverages (SSBs and non-SSBs)

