The objective of this study is to conduct one of the first field experiments to assess the degree to which sugary drink warning labels encourage adolescents to reduce their intake in a country that does not yet have any front-of-package food labeling regulations. We will also evaluate whether a graphic-based warning label is more effective compared to a text-based warning label.

Primary outcome variable(s)

The primary outcome will be mean ounces of sugary beverages purchased based on sales data, which will include the date of the transaction and the type of food or beverage sold (e.g., diet soda, lemonade) along with the item brand, size, quantity, and price.

Secondary outcome variable(s)

Our secondary outcomes will be the total kilocalories (kcal) purchased at the school store based on the surveys we collect. A measure of total calories purchased will allow us to assess whether adolescents who buy fewer sugary drinks compensate by buying other snack foods. We define a sugary drink as any non-alcoholic beverage that lists any form of caloric sugar-based sweetener as an ingredient (this would not include 100% juice). We will also record the presence and type of food/beverage marketing in the store.

Background

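### The SAP names two primary outcomes but gives no success rule, testing order or multiplicity adjustment, and the protocol's Holm rule does not clearly carry over to them.

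*SAP*

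**What the plan says.** The protocol (Primary outcome variable(s)) names a single primary: "The primary outcome will be mean ounces of sugary beverages purchased based on sales data".

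The SAP (Primary outcomes) lists two, "Fluid ounces of SSBs purchased per sales transaction" and "Total beverage calories purchased per sales transaction". Its Hypotheses section gives each a separately numbered, directional hypothesis: "SSB warning/non-SSB promotion posters are associated with greater reduction in mean fluid ounces of SSB purchased" and "SSB warning/non-SSB promotion posters are associated with greater reduction in total beverage calories purchased".

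Under Statistical analysis, the SAP's difference-in-differences equation has one response variable, so two outcomes mean two fitted models and two p-values. The null hypothesis is a zero interaction coefficient, described as "indicating no change in the fluid ounces of SSBs purchased and beverage calories purchased between conditions". The SAP does not state a significance level, an order of testing, an adjustment, or whether one or both results are needed to declare success.

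The only multiplicity rule is in the protocol's Analysis Plan: "A Bonferroni-holm correction will be applied to control for multiple comparisons". The sentence immediately before it reads: "Primary and secondary outcomes in the calorie, text-based warning label, and graphic warning label arms will each be compared to one another". The SAP does not repeat, extend or withdraw that rule. Its primary analysis (Description of data) uses one treatment school and one control school.

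**The concern.** With two primary outcomes, two hypotheses and two p-values, an analyst following the SAP has two unadjusted chances at a primary claim. The second was added after a protocol that had only one.

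The protocol's Holm rule would close the gap if it applied, but its natural family is the set of pairwise contrasts among three label arms. The SAP's primary analysis has one contrast per outcome, so on that reading there is nothing to adjust. On a wider reading Holm spans the outcomes as well. Because the SAP is silent, the choice between the readings can be made after the p-values are known.

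**Working it through.** **Inputs from the documents.** Two primary outcomes, two numbered hypotheses and one treatment-control contrast per outcome (SAP). One primary outcome and a Holm rule whose family of tests is not defined (protocol).

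**Inputs that are assumed.** Two-sided alpha of 0.05 per test; the correlation ρ between the two test statistics; either outcome suffices for a claim; each test holds its nominal level. The documents give none of these.

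**Step 1. Is 5% a reasonable alpha to assume?** The only related figure is in the protocol (Accrual): 82% power for all differences to be significant at 0.21 SD with 500 students per condition.
- One pairwise test: 0.21/√(2/500) = 3.32, so power at two-sided 0.05 is Φ(3.32 − 1.96) = 91.3%. This is not the stated figure.
- All three pairwise tests significant, with means at 0, 0.21 and 0.42 SD and no clustering (simulation): 82.6% at unadjusted two-sided 0.05, and 82.5% with Holm. Both reproduce 82%.
- One pairwise test at 0.05/3: 82.3%, which also reproduces it.

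The stated power is therefore consistent with a two-sided 5% level. It does not establish that level for the SAP, which describes a different comparison.

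**Step 2. Family-wise error with two unadjusted tests, both nulls true.**
- Any false significance: 1 − P(|Z₁| ≤ 1.96 and |Z₂| ≤ 1.96), with (Z₁, Z₂) bivariate normal with correlation ρ. At ρ = 0 this is 1 − 0.95² = 9.75%. The upper bound is 0.05 + 0.05 = 10%.
- False reductions only, since both hypotheses predict a reduction: the same calculation with one tail of 0.025 per test. At ρ = 0 this is 1 − 0.975² = 4.9%. The comparator is 2.5% for a single test.

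| ρ (assumed) | Any false significance (one test: 5%) | False reduction only (one test: 2.5%) |
|---|---|---|
| 0 | 9.75% | 4.9% |
| 0.5 | 9.1% | 4.5% |
| 0.7 | 8.3% | 4.2% |
| 0.8 | 7.8% | 3.9% |
| 0.9 | 7.0% | 3.5% |
| 0.95 | 6.5% | 3.2% |
| 0.99 | 5.7% | 2.8% |

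For ρ from 0.9 down to 0, both columns are about 1.4 to 2 times the single-test rate (7.0/5 = 1.4; 9.75/5 = 1.95; 4.9/2.5 = 1.96).

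**Step 3. Other success rules.** If both outcomes had to be significant, the error would be at most 5% with no adjustment. If each test is run at 0.025, the two-sided family-wise error is 4.9% at ρ = 0, 4.7% at 0.5, 4.0% at 0.8 and 3.6% at 0.9. Holm gives the same values when both nulls are true.

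**Step 4. What these figures leave out.** The SAP compares one school with one school on transaction data and states no clustering correction, although the protocol's Analysis Plan has one based on the intraclass correlation. As an illustration only, an ignored variance inflation of 2 gives an effective cut-off of 1.96/√2 = 1.39. The per-test error is then about 17%, and for two independent tests about 30% (1 − 0.834² = 0.304).

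**The case against.** A reader might infer that the plan's false-claim rate is 7 to 10% instead of 5%. The documents do not support that as a flat statement, for four reasons.

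- **Direction.** Both hypotheses predict a reduction, so a significant increase would not support the posters. Counting reductions only, the rate stays below 5% at every correlation shown. This stands, and the directional figures belong beside the others. The inflation remains, because the fair comparator is then 2.5%.
- **Success rule.** The SAP never says that either outcome suffices. It states one aim covering both outcomes and joins them with "and" in the description of the null. Requiring both would hold 5%, and treating each hypothesis as its own question at 5% is a defensible position. But that conjunction only describes the null. It is not a both-must-succeed rule, and the numbered hypotheses leave a claim on either one open.
- **Alpha and correlation.** Neither is stated. SSB calories are part of total beverage calories and both outcomes come from the same transactions, so the correlation may well be high and the 10% end is unlikely. Against that, the calorie outcome also counts non-SSB drinks, so switching to other caloric drinks could separate the two.
- **Actual error rate.** School-level effects with one school per arm are a larger problem, and no multiplicity sentence cures them. This stands, so the figures are the multiplicity component only.

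A second tempting reading is that the protocol's Holm rule definitely adjusts nothing here. That is too firm. The preceding sentence mentions primary and secondary outcomes, the family is undefined, and the SAP does not withdraw the rule. What can be said is that the rule does not clearly carry over.

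**Conclusion.** The gap holds in a conditional form. The SAP has two primary outcomes with separate hypotheses and tests, and no success rule, order or adjustment. The protocol's Holm rule was written for three-arm comparisons with one primary outcome and leaves the matter open. Followed as written, the SAP allows two unadjusted tests, with roughly 1.4 to 2 times the single-test error for correlations from 0.9 down to 0. That size rests on two-sided 5% tests, an either-suffices reading, the assumed correlations and valid individual tests. The need for a stated rule does not depend on the exact size. The point should be corrected, but it ranks below the problem of having one school per arm.

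**What to change.** In the SAP's Primary outcomes and Statistical analysis sections, state a two-sided alpha of 0.05 and adopt one of two rules:

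1. Apply the protocol's Holm correction across the two primary outcomes: the smaller p-value against 0.025 and, if that is significant, the larger against 0.05.
2. Test ounces, the protocol's primary outcome, first at 0.05, and beverage calories at 0.05 only if ounces is significant.

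**Cost.** Either rule takes a sentence or two and no new data. Under Holm the first threshold falls from 0.05 to 0.025, so two p-values both between 0.025 and 0.05 would support no claim. Under the fixed sequence ounces loses nothing, but beverage calories cannot be claimed if ounces fails. Either rule controls multiplicity only to the extent that each test is valid, so the clustering question needs its own answer.
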